## 2 ELIGIBILITY ASSESSMENT AND ENROLLMENT

### 2.1 ELIGIBILITY CRITERIA

#### 2.1.1 Inclusion Criteria

2.1.1.1 Age  $\geq$  18 years.

- 2.1.1.2 Ability of subject to understand and the willingness to sign a written informed consent document.
- 2.1.1.3 Subject must be also enrolled on an NCI allogeneic transplant protocol.
- 2.1.1.4 Patients must agree to practice effective contraception (both male and female subjects, if the risk of conception exists). The effects of ECP on the developing human fetus are unknown. For this reason and as well as other Methoxsalen used in this trial is in a class of agents that is known to be teratogenic, men must agree to use adequate contraception (hormonal or barrier method of birth control; abstinence) prior to study entry and for the duration of study participation, and for 4 months after the completion of study treatment. Should a woman become pregnant or suspect she is pregnant while her partner is participating in this study, she should inform her treating physician immediately.

## 2.1.2 Exclusion Criteria

- 2.1.2.1 Any physical or mental condition that, in the opinion of the PI, would cause the risk/benefit ratio of participation to be unacceptable.
- 2.1.2.2 Inclusion of ECP in the treatment of any patient is contraindicated by any of the following:
  - Unstable hemodynamics requiring vasopressors or other support measures not amenable to or medically appropriate for continuation during the procedure.
  - Uncontrolled infection.
  - Inability to maintain acceptable venous access.
  - Uncontrolled or uncorrectable coagulopathy.
- 2.1.2.3 Pregnant women are excluded from ECP because methoxsalen, an agent utilized for the study procedure, may cause fetal harm. Because there is an unknown but potential risk for adverse events in nursing infants secondary to treatment of the mother with methoxsalen, breastfeeding should be discontinued if the mother is treated with methoxsalen. Pregnancy will be evaluated prior to initiation of ECP.
- 2.1.2.4 History of allergic or idiosyncratic/hypersensitivity reactions to 8-methoxypsoralen/psoralen compounds.
- 2.1.2.5 History of a light-sensitive cutaneous disease
- 2.1.2.6 Subjects with aphakia

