### Eligibility:

- Adult patients on an NCI allogeneic transplantation protocol.

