### Design:

- Non-randomized, single institution study.
- Research blood for biomarkers will be collected on all patients enrolled.
- ECP will be offered as an addition to investigator chosen treatments in patients who develop steroid refractory acute GVHD.
- The study will enroll a total of up to 450 patients.

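### Three methoxsalen contraindications (items 2.1.2.4 to 2.1.2.6) are written as exclusions from the whole biomarker study, while the neighbouring ECP items bar only ECP

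*Combined protocol and SAP*

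**What the plan says.** The Precis gives the population as "Adult patients on an NCI allogeneic transplantation protocol". Its design paragraph has research blood taken from everyone enrolled and adds that "ECP will be offered as an addition to investigator chosen treatments in patients who develop steroid refractory acute GVHD". ECP is therefore a later, optional branch for a subset.

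Section 2.1.2 is the exclusion list for the study as a whole. Two of its items limit themselves to ECP in words:
- 2.1.2.2 opens with "Inclusion of ECP in the treatment of any patient is contraindicated by any of the following".
- 2.1.2.3 says "Pregnant women are excluded from ECP because methoxsalen, an agent utilized for the study procedure, may cause fetal harm".

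The next three carry no such limit:
- 2.1.2.4: "History of allergic or idiosyncratic/hypersensitivity reactions to 8-methoxypsoralen/psoralen compounds"
- 2.1.2.5: "History of a light-sensitive cutaneous disease"
- 2.1.2.6: "Subjects with aphakia"

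Sections 1.2.5 and 10.1 name all three conditions as reasons not to give methoxsalen, and Section 10.2 repeats psoralen hypersensitivity as a bar to the procedure. On timing, Section 2.1.2 states only that "Pregnancy will be evaluated prior to initiation of ECP". In the Section 3.3 calendar, the pregnancy test is the only eligibility test in the ECP columns.

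**The concern.** The main aims in Sections 1.1.1 and 8 are to see whether biomarkers predict acute GVHD, steroid refractoriness and the outcome of second-line therapy with and without ECP. Except in the with-ECP group, these need blood samples and follow-up but no methoxsalen. A patient with aphakia, for example, has no stated reason to be refused a blood draw, and if steroids later failed would belong in the no-ECP second-line group that the primary objective names. As written, that patient cannot enrol.

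What is at stake is whether the enrolled cohort matches the population in the Precis, and whether staff completing the eligibility checklist all decide such cases in the same way. One may apply the list literally; another may read the three items as ECP criteria because the two items before them are.

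**Working it through.** The point turns on wording, so there is no plan figure that it contradicts. The check has four parts.

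**1. Scope of each item in Section 2.1.2**

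| Item | Condition | Limited to ECP in words? |
|---|---|---|
| 2.1.2.2 | unstable haemodynamics, uncontrolled infection, no venous access, coagulopathy | yes |
| 2.1.2.3 | pregnancy | yes |
| 2.1.2.4 | psoralen reaction | no |
| 2.1.2.5 | light-sensitive skin disease | no |
| 2.1.2.6 | aphakia | no |

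The only rationale found for the last three is methoxsalen (Sections 1.2.5 and 10.1). No section ties them to blood sampling, to acute GVHD or to steroid response.

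**2. Share of enrolees for whom the three items are relevant**

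- Section 8, final paragraph: up to 100 patients evaluable for ECP analyses under a ceiling of 450. 100/450 = 22.2%, so 77.8% never receive ECP.
- Section 8, item 2: illustrations with 22 or 34 ECP recipients, against about 400 enrolled. 22/400 = 5.5% and 34/400 = 8.5%, so 94.5% or 91.5% never receive ECP.

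**3. Number of patients lost**

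The documents give no prevalence for the three conditions. Assume 1% to 3% in total.

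- Of 400 expected enrolees: 0.01 × 400 = 4 to 0.03 × 400 = 12.
- Developing acute GVHD, at Section 8's 160/400 = 40%: 1.6 to 4.8.
- Steroid refractory, at Section 8's one half: 0.8 to 2.4, that is about 1 or 2.

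A wider assumption of 0.5% to 5% gives 2 to 20 of 400.

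**4. Effect on power**

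Section 8, item 1 claims 80% power for 44 versus 44, effect size 0.75, two-sided alpha 0.01. For a two-sample t-test with n per group, the degrees of freedom are 2n − 2 and the noncentrality is d√(n/2) = 0.75 × √22 = 3.52. The result is 80.9%, which reproduces the plan's figure. Shrinking both groups gives:

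| Loss | Power |
|---|---|
| none | 80.9% |
| 1% | 80.4% |
| 3% | 79.4% |
| 5% | 78.3% |

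The loss of power is negligible at any plausible prevalence.

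**The case against.** **Comparability.** Requiring every enrolee to be free of lasting ECP contraindications could make the with-ECP and without-ECP groups more alike. The protocol does not follow that logic. Patients who are unstable, infected, coagulopathic or pregnant may enrol and are barred only from ECP. A drafter might have meant to separate lasting conditions from passing ones, but the documents do not say so. Section 8 also leaves the choice of ECP to the investigator on any criteria, and its illustrated ECP analysis lies within ECP recipients. This defence fails.

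**Conflict with the enrolment estimate.** A reader might infer that the three items contradict Section 8's expectation that about 90% of transplanted patients enrol. They do not. That estimate leaves about 45 of 450 unenrolled, and a loss of 1% to 3% fits within it. A one-line Precis population is also normally narrowed by exclusion criteria.

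**Missed checks before ECP.** A reader might infer from the calendar that these conditions are assessed once at registration and never again, perhaps months before ECP. The documents do not support this. Section 10.1 attaches all three conditions to methoxsalen use itself, and for light-sensitive disease to its initiation. Section 3.2.2 places ECP under a department standard operating procedure, a physician's direction and the manufacturer's recommendations, and that procedure is not in the documents. Section 2.3.1 allows entry at any point of the transplant course, so the interval may be short. What stands is narrower: the calendar's ECP columns name only the pregnancy test.

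**Small practical effect.** Section 8 declares every analysis exploratory. Section 3.1 reports accrual suspended, 5 patients enrolled and all off study, and no new enrolment. It also says resources are being explored that would let accrual begin again. The effect is small, and a reopening amendment would be the natural time for the change.

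**Conclusion.** The point holds as an inconsistency of scope. Items 2.1.2.4 to 2.1.2.6 exclude from the whole study on grounds that the documents link only to methoxsalen, while 2.1.2.2 and 2.1.2.3 exclude from ECP alone. Whether this was intended is not stated; a drafting gap is plausible. Most enrolees are screened on criteria irrelevant to them: about 78% at Section 8's maximum for ECP, over 90% on its illustrations.

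The cost in patients is about 4 to 12 of 400, with about 1 or 2 from the steroid refractory group. This rests on an assumed 1% to 3% prevalence and on Section 8's rates of acute GVHD and steroid failure. A reader might infer material bias in the no-ECP group or a real loss of power; numbers of this size support neither. The harm is to the stated scope, to generalisability and to consistent enrolment decisions. On timing, the finding is only that three sections need to agree, not that a check is absent.

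**What to change.** Reword 2.1.2.4, 2.1.2.5 and 2.1.2.6 so that, like 2.1.2.2 and 2.1.2.3, they bar ECP and not enrolment. Affected patients could then enrol for biomarkers and be followed in the no-ECP group. The methoxsalen contraindications in Sections 1.2.5, 10.1 and 10.2 stay as they are. If exclusion from the whole study is intended, Section 2.1.2 should say so and give the reason.

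Reconcile Sections 2.1.2, 3.3 and 10.1 on when these conditions are confirmed, citing the department procedure if that is where it happens.

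The cost is a rewording of three criteria, the matching change to the eligibility checklist, and a cross-reference. It adds no procedure for patients who do not receive ECP and needs no change to the sample size.

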## 2.2 SCREENING EVALUATION

- 2.2.1 The following will be documented prior to protocol entry.
  - Concurrent participation in an ETIB allogeneic transplant protocol.

## 2.3 REGISTRATION PROCEDURES

Authorized staff must register an eligible candidate with NCI Central Registration Office (CRO) within 24 hours of signing consent. A registration Eligibility Checklist from the web site (<http://home.ccr.cancer.gov/intra/eligibility/welcome.htm>) must be completed and sent via

encrypted email to: NCI Central Registration Office [[contact]](mailto:[contact]). Verification of Registration will be forwarded electronically via e-mail to the research team. A recorder is available during non-working hours.

### 2.3.1 Patient Assignment or Stratification Procedure

[figure not shown]
Patients will be enrolled based on their participation on any NCI allogeneic transplant protocol. Specific treatments for steroid refractory acute GVHD, including the use of ECP, will be at the discretion of the patient's primary transplant protocol PI (or designee) in consultation with the PI of this protocol. Patients will not be randomized or otherwise assigned. Patients may enter the protocol at any point during their participation on a separate NCI transplant protocol and absence of any biomarker time point(s) will be noted but will not constitute a deviation from this protocol.

## 3 STUDY IMPLEMENTATION

### 3.1 STUDY DESIGN

Please note that as of January 27, 2017 Accrual has been suspended on this protocol. Amendment D (version date: 10/02/2018) serves as the formal notification to the IRB of an Administrative Hold pending delivery of a new ECP device. Potential resources are being explored that would allow the protocol to begin to accrue in the future. No new patients will be enrolled. We enrolled total of 5 patients on this study, all 5 patients have completed the follow up period and are off study.

## Schema

Subjects will be followed according to the schedule outlined in section 3.3 for either three months post transplant (D+100), six months post transplant, or six months following the last ECP procedure. A final assessment will be completed prior to removing the subject from the study. Biomarker time points will commence when the patient is enrolled and enrollment at any point of the patient's transplant is allowed.

### 3.1.1 Diagnosis of steroid refractory acute GVHD

Diagnosis of steroid refractory acute GVHD in any patient will be defined at a minimum as clinical worsening despite 3 days, no clinical response despite 7 days, or an inadequate clinical response despite 14 days of methylprednisolone IV (or equivalent corticosteroid) at a minimum dose of 2mg/kg/day.

- Clinical responses are determined by measurements specific to the organ(s) affected.

- The determination of an inadequate clinical response to steroids will be made by the PI of the patient's primary transplant protocol (or their designee) in consultation with the PI of this protocol.
- General guidelines to be used for this determination by system will be as follows:
  - GI: failure to show at least a 50% reduction in stool volume compared to the highest daily stool volume.
  - SKIN: failure to show at least a 50% improvement of skin rash severity or distribution compared to the worst severity or extent of the rash.
  - LIVER: failure to demonstrate at least a 50% reduction in direct bilirubin compared to the peak preceding value.

### 3.2 EXTRACORPOREAL PHOTOPHERESIS (ECP)

#### 3.2.1 Schedule of ECP treatments

Patients who have ECP included in their treatment of steroid refractory acute GVHD will in general follow this recommended schedule:

- Twice weekly for 1 month
- Twice every other week for 2 months
- Twice during one week per month for 4 months for a total of up to 7 months of treatment

The frequency or duration of therapy can be individualized at PI discretion based on clinical risk and potential benefit of the variation. The rationale for the variation should be clearly documented in the study note of patient's medical record.

#### 3.2.2 ECP Procedure

Patients who will undergo ECP will be treated according to the standard operating procedure of the Clinical Center Department of Transfusion Medicine. The procedure may be done in a hospital room, an outpatient department, or in DTM

The UVAR will be used to perform therapeutic ECP under the direction of a Department of Transfusion Medicine (DTM) physician, in accordance with specific NIH Clinical Center Protocols, and the Medical Chief of Blood Services Section (BSS). Unless otherwise stated, the apheresis staff will adhere to the manufacturer's recommendations when performing ECP.

Registered Nurses will perform ECP as ordered by DTM physicians in the Clinical Research Information System (CRIS). The Operator's Manual for the UVAR and the directions for use with the apheresis kit will be followed at all times.

If the patient lacks adequate existing venous access for ECP, they may need to have a catheter placed by Interventional Radiology or the VAD Service.

### 3.3 STUDY CALENDAR

Procedure	Baseline / Enrollment (+/- 2 days)	At D0 of transplant	If no acute GVHD or steroids, collect at D100 (+/- 1 week)	At diagnosis of acute GVHD (+/- 1 week)	At diagnosis of steroid refractory or responsive acute GVHD (+/- 1 week)	If acute steroid refractory GVHD with no ECP, collect at 6 months post transplant (+/- 1 month)	ECP Only	
							At first ECP of each month of treatment	At 6 months from last ECP (+/- 1 month)
Study Note	X		X	X	X	X	X	X
TBNK	X	X	X	X	X	X	X	X
Urine or serum <math>\beta</math>HCG in women of childbearing potential							X	
Biomarkers	X	X	X	X	X	X	X	X
GVHD Evaluation				X	X	X	X	X
ECP Adverse Events							X	X
GVHD Meds		X		X	X	X	X	X

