#### **1.1.2 Secondary Objective**

To study steroid requirement, GVHD outcome, and overall survival at 6 months in patients with acute GVHD.

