### 6.2.2 Measurement of GVHD Outcome and Response

Patients will be followed for outcome using overall survival, GVHD free survival, and steroid free survival at either 3 months post-transplant (D+100), 6 months post-transplant, or 6 months after the last ECP procedure. The definitions of GVHD response that will be used are outlined in an American Society for Bone Marrow Transplantation consensus statement.

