## **8 STATISTICAL CONSIDERATIONS**

The primary objectives of this trial are to determine, in an exploratory fashion, if any information obtained from biomarkers in patients who undergo allogeneic transplantation may be used to predict whether patients will develop acute GVHD. In addition, it will be used to determine if biomarkers obtained from patients with acute GVHD may be used to predict steroid refractoriness and the outcome of investigator chosen therapies for steroid refractory disease with and without ECP. As secondary objectives, the study will evaluate acute GVHD outcome, overall survival at 6 months, and steroid use.

This study is intended to be a companion trial to other efforts in the ETIB by collecting information on a set of acute GVHD biomarkers at various times throughout the course of an allogeneic transplant. In order to allow for a large enough number of patients to conduct a series of analyses at several main points, the study will have an accrual ceiling of 450 transplanted, of which approximately 200 patients would be expected to develop acute GVHD.

It will be estimated that approximately 90% of 450 NCI patients who are transplanted over a 10 year period will enroll on this trial, and of that approximately 400 patients, 160 will develop aGVHD and 240 will not. As noted in the schema and sections 3.3 of the protocol, biomarkers will be collected on patients at various times, starting with collections at enrollment and just prior to transplantation. If a large set of biomarkers at baseline is able to predict 80% of those who develop aGVHD and 80% of those who do not develop aGVHD, then these estimates could be made with 95% two sided confidence intervals of 73.3% to 85.7 and 74.6% to 84.7% respectively. If we are able to actually obtain such a large enough number of patients, the results could also be divided into two groups to allow for 50% of patients to train the prediction classifier and 50% to test the prediction.

With up to 165 patients maximally available with acute GVHD, the following analyses could be undertaken.

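### Steroid-responsive acute GVHD patients have no dated GVHD or steroid assessment after response is declared, although the secondary objective covers all acute GVHD patients at 6 months

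*Combined protocol and SAP*

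**What the plan says.** Section 1.1.2 gives the secondary objective as "To study steroid requirement, GVHD outcome, and overall survival at 6 months in patients with acute GVHD". Section 8 repeats it: "the study will evaluate acute GVHD outcome, overall survival at 6 months, and steroid use". Neither place restricts it to refractory disease, and neither says from what date the 6 months run.

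The calendar in section 3.3 has these columns after the acute GVHD diagnosis visit, or for patients without one:

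- "At diagnosis of steroid refractory or responsive acute GVHD (+/- 1 week". GVHD Evaluation and GVHD Meds are both marked.
- "If no acute GVHD or steroids, collect at D100 (+/- 1 week". Study Note, TBNK and Biomarkers are marked; GVHD Evaluation and GVHD Meds are not.
- "If acute steroid refractory GVHD with no ECP, collect at 6 months post transplant (+/- 1 month". GVHD Evaluation and GVHD Meds are marked.
- Two columns for ECP patients only: the first procedure of each treatment month, and "At 6 months from last ECP (+/- 1 month". Both rows are marked in each.

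The general text is looser. Under the Schema heading in section 3.1: "Subjects will be followed according to the schedule outlined in section 3.3 for either three months post transplant (D+100), six months post transplant", with 6 months after the last ECP as the third option, plus an undated final assessment before a subject leaves the study. Section 6.2.2 reads overall survival, GVHD-free survival and "steroid free survival at either 3 months post-transplant (D+100), 6 months post-transplant, or 6 months after the last ECP procedure". Section 3.4.2 lists the same three evaluations as the way to complete the study. None of the three sections says which time applies to which patients.

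**The concern.** The objective and the calendar describe different populations. The objective is about everyone with acute GVHD. The calendar's late columns are conditional, and none of the conditions admits a patient who has had acute GVHD, was given steroids and responded. That patient's last calendar entry is the visit that classifies the response, which is not a 6-month outcome visit.

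At stake are the GVHD and steroid parts of the secondary objective. If staff follow the column rules, those endpoints are recorded late only in patients whose steroids failed. Any 6-month summary for acute GVHD patients would then be missing the better-prognosis group, and the missingness would be built into the schedule.

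**Working it through.** **Step 1. Match each late calendar column to each group.**

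| Group | D100 column | 6-month post-transplant column | ECP columns | Last dated GVHD and steroid record |
|---|---|---|---|---|
| Steroid responder | No: has had both GVHD and steroids | No: refractory only | No | Response declaration |
| Refractory, no ECP | No | Yes | No | 6 months post-transplant |
| Refractory, ECP | No | No | Yes | 6 months after last ECP |
| Acute GVHD, no steroids | Depends on how the label is read | No | No | GVHD diagnosis |

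The D100 label can mean neither GVHD nor steroids, or the absence of one of them. A responder is excluded on both readings.

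**Step 2. How early the responder's last entry falls.** Section 3.1.1 declares refractoriness after 3, 7 or 14 days of steroids. Assume response is declared on the same clock. With the calendar's one-week window, the last entry is at most 14 + 7 = 21 days after steroids start.

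**Step 3. Does the general text supply a later time?** Its three end times correspond to the calendar's three end columns, and the Schema text sends the reader back to section 3.3. The final assessment it promises has no date and no listed content. So the text promises follow-up but does not place a responder at any particular time.

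**Step 4. The time origin.** The 6-month clock starts at transplant in one calendar column and at the last ECP in another. In section 8, item 2, it starts when the patient is found refractory. With up to 7 months of ECP (section 3.2.1), the ECP patient's final visit can fall 7 + 6 = 13 months after ECP begins. ECP patients do have monthly GVHD and medication records during treatment, but none fixed at 6 months from a common origin.

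**Step 5. Number of patients affected.** The plan's own count first: 450 × 0.45 = 202.5, against about 200 stated in section 8. Section 8 also gives 160 of about 400 enrolled. Responders = acute GVHD patients × (1 − refractory share):

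| Refractory share | Source | Of 160 | Of 200 |
|---|---|---|---|
| 50% | Section 8; upper end of section 1.2.1 | 80 | 100 |
| 40% | Lower end of section 1.2.1 | 96 | 120 |
| 30% | Precis | 112 | 140 |

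The share without a dated late GVHD or steroid record is therefore 50% to 70%. These counts treat every acute GVHD patient as steroid-treated.

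**Step 6. Direction of the selection.** Section 1.2.3 quotes non-relapse mortality of 27% in day-5 steroid responders and 49% in non-responders, a gap of 49 − 27 = 22 points. This shows only that prognosis differs between the groups. It uses another endpoint and another definition of response, with no time horizon given.

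**Step 7. Precision.** The worst-case 95% half-width for a proportion is 1.96 × √(0.25/n). At the even split, recording the outcome in all acute GVHD patients takes n from 100 to 200 and the half-width from 9.8 to 6.9 points. On the lower count, n goes from 80 to 160 and the half-width from 11.0 to 7.7.

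**The case against.** The strongest reply is that follow-up is promised to everyone. Section 6.2.2 follows patients for outcome without naming a subgroup, section 3.4.2 makes one of the three evaluations the route to completion, and the Schema text requires a final assessment. On that view the fault is an unassigned time point. This stands in part: follow-up is not absent from the plan. But a site working from the calendar has no date at which to do it for a responder and no instruction on what to record.

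The schema figure is not visible in the text reviewed, and it may route responders to D+100 or to 6 months. If so, the calendar contradicts it and the two need reconciling.

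A reader might go further and infer that 6-month survival cannot be estimated in acute GVHD patients. The documents do not support that. Every subject is also on an NCI transplant protocol (section 2.1.1.3), and section 5.2.1 refers to treatment outcomes held in the clinical records. Vital status may well be obtainable, although the plan does not say it will be taken from there.

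A reader might also infer that the responsive-versus-refractory comparison has no common time. It does: section 8, item 1 compares biomarkers at baseline or as change from baseline, and both groups share one calendar column. Nor can it be said that acute GVHD patients not given steroids have no further contact, because the D100 label may include them.

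Finally, the study is exploratory. Section 3.1 reports accrual suspended since January 2017, with all 5 enrolled patients off study. That limits the practical weight, but an exploratory summary still needs its outcome recorded in the population it describes.

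**Conclusion.** The point holds for the GVHD and steroid endpoints. Followed as printed, the calendar gives steroid responders no dated GVHD evaluation or GVHD medication record after response is declared. They are about half of acute GVHD patients by section 8 (80 to 100 of 160 to 200) and up to 70% by the Precis (112 to 140). Scheduled 6-month data on those endpoints would come only from refractory patients. Survival is less affected.

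It is tempting to mix the 27% and 49% mortality figures and quote a bias of 11 to 15 points (49 − 38.0 at a 50/50 mix, 49 − 33.6 at 70/30). The documents do not support that as an estimate, for the reasons in step 6, and also because no section plans to report a refractory-only figure as one for all acute GVHD.

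The conclusion assumes that the printed column conditions are applied as written and that the unseen schema figure does not override them. It has practical effect only if accrual restarts.

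**What to change.** - Relabel the 6-month post-transplant column so that it covers every acute GVHD patient not receiving ECP: responsive, refractory, or not needing steroids.
- For every acute GVHD patient, ECP patients included, record vital status, GVHD status and steroid dose at one common 6-month time. State its origin, for example transplant or acute GVHD diagnosis. Where there is no visit, abstract these from the primary transplant protocol's records, and say so in the plan.
- State whom the D100 column covers. If it includes acute GVHD without steroids, mark GVHD Evaluation and GVHD Meds there.
- Align sections 3.1 (with the schema), 3.3, 3.4.2 and 6.2.2, so that each group has one named end time.

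The cost is a calendar amendment, some chart abstraction and at most one extra research sample per responder. The changes concern data collection only. They should be made before any restart of accrual.
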